#### ***Analysis of adverse events of special interest (AESI)***

Summaries of AESI defined by the search criteria:

- All treatment emergent AESIs, by AESI category and PT, showing number (%) of patients, sorted by decreasing incidence of PT within each AESI category.

- Within each treatment emergent AESI category, at a minimum the data display will include:
  - Overview summary
  - Treatment duration summary
  - Incidence by patient and by event
  - Serious TEAEs
  - TEAEs leading to treatment discontinuation
  - TEAEs leading to death
  - Possibly related TEAEs

The number at risk and the number with events will be provided by visit and treatment group

#### ***Analysis of adjudicated CV events***

The following CV event summaries will be generated for the safety population:

- MACE (primary) and MACE (narrow), showing number (%) of patients with at least one adjudicated treatment-emergent CV event and number of such events per 100 patient-years (number of events adjusted for the total duration of exposure).
- All adjudicated treatment-emergent CV events by CV events categories, showing number (%) of patients with at least one adjudicated treatment-emergent CV event and number of events per 100 patient-years, sorted by alphabetical order.
- All events undergone adjudication, all events adjudicated as non-CV event, and all events that are not evaluable, showing number (%) of events (patients).

Summary describing the investigator-reported treatment-emergent SAE and the associated CAC adjudication classification will be provided.

#### **2.4.4.2 Deaths**

The incidence of death and number of death per 100 patient-years (number of death adjusted for the total duration of exposure) will be generated on the safety population. The following deaths summaries will be generated on the safety population.

- Number (%) of patients who died by study period (on-treatment, during follow-up or post-study)
- TEAE leading to death (death as an outcome on the AE CRF page as reported by the Investigator) by primary SOC , HLGT, HLT and PT showing number (%) of patients sorted by internationally agreed order of SOC and alphabetic order of HLGT, HLT, and PT.

Listings will be provided for all deaths with flags indicating on-treatment, during follow-up or post-study status.

### **2.4.4.3 Analyses of laboratory variables**

The summary statistics (including number, mean, median, standard deviation, minimum and maximum) of all laboratory variables (central laboratory values and changes from baseline) will be calculated for each visit or study assessment (baseline, each post baseline time point, and endpoint) by treatment received. This section will be organized by biological function as specified in [Section 2.1.3.3](#).

The incidence of PCSAs (list provided in [Appendix C](#)) at any time during the TEAE period will be summarized by biological function and treatment received whatever the baseline level and/or according to the following original baseline status categories:

- Normal/Missing
- Abnormal according to PCSA criterion or criteria

The incidence of abnormal laboratory values at any time during the TEAE period will be summarized in shift tables by biological function and treatment group whatever the baseline level and/or according to the following original baseline status categories:

- Normal/Missing
- Abnormal high according to the normal range
- Abnormal low according to the normal range

In addition, for all laboratory parameters, the mean change from baseline at each scheduled visit during the double-blind treatment period will be plotted by treatment groups.

Time to onset of the first G3 or G4 neutropenia (absolute neutrophil count <1.0 Giga/L) in LTS11210, and time to onset of the first platelet count <100 Giga/L in LTS11210 will be analyzed using Kaplan-Meier estimates, using the midpoint of the time interval between the first assessment showing the elevation and the previous assessment, presented by previous treatment prior to enrollment into LTS11210. Further analyses will be in the report of integrated summary of safety.

Listings will be provided with flags indicating the out-of-range values as well as the PCSA values.

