## 12 STUDY PROCEDURES

### 12.1 VISIT SCHEDULE

It is preferred that all study visits take place in the morning. Some visits that include only scheduled blood sampling (V3, V5, V6.1) (Week 2, Week 6, and Week 10) can be scheduled as Home Visits or clinic visits.

Patients will be considered as having completed their treatment per protocol and should complete the end of treatment visit (EOT):

- At Week 264, if sarilumab has been commercialized in their country at that time. EOT visit should be performed instead of Week 264 visit and the assessments defined in the flowchart ([Section 1.2.1](#), [Section 1.2.2](#)) should be completed.
- At any visit after Week 264 once sarilumab is commercialized in their country (applicable for patients in the countries where commercial sarilumab is not available at the time the patients completed their Week 264). Some of the assessments are NOT required at EOT for these patients; please refer to the flowchart ([Section 1.2.1](#), [Section 1.2.2](#)) for details.
  - When commercialization occurs in a given country, investigators in that country will be alerted by the Sponsor and they will inform their patients during the next scheduled study visit that their subsequent visit 12 weeks later will be the EOT visit.
- At any visit after Week 264 at the time the study is closed in 2020 in countries where commercialization has still not occurred. Some of the assessments are NOT required at EOT for these patients; please refer to the flowchart ([Section 1.2.1](#), [Section 1.2.2](#)) for details.
  - EOT visits for all patients remaining in the study at that time will occur at scheduled clinic visits over a 3-month period in order to stagger the completion of EOT visits across the study, and allow the completion of the 6-week follow up period for all patients prior to study closure. Investigators will be alerted by the Sponsor that the study closure is approaching and they will inform their patients during the next scheduled study visit that their subsequent visit 12 weeks later will be the EOT visit.
- At Week 264, for patients in the UK no matter when the sarilumab is commercially available in the country. EOT visit should be performed instead of Week 264 visit and assessments defined in the flowchart ([Section 1.2.1](#), [Section 1.2.2](#)) should be completed.

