**12.1.11 Visit 30 (Week 288), Visit 32 (Week 312), Visit 34 (Week 336), Visit 36 (Week 360), Visit 38 (Week 384), Visit 40 (Week 408), Visit 42 (Week 432), Visit 44 (Week 456), Visit 46 (Week 480), Visit 48 (Week 504): On treatment visits from Week 288 to week 504**

This section refers to on-treatment visits with less complex clinical assessments, for patients who are continuing in the study after week 264 because sarilumab is not yet commercialized in their country.

The Investigator will:

- Check compliance to the study drug and concomitant medication and record any changes in the patient's CRF.
- Record vital signs including body temperature, blood pressure, HR and body weight.
- Physical examination will be done only at weeks: 288, 336, 384, 432 and 480.
- Tuberculosis assessment. In case of suspicion of tuberculosis, refer the patient to a TB specialist for complete examination and additional work-up (see specific instructions in [Section 10.2.1](#)).

- Inquire regarding AE/SAEs.
- Obtain (fasting) blood for complete clinical laboratory determinations including:
  - hematology
  - clinical chemistry profile
  - LFTs (no PT required)
  - lipids (only TC, HDL cholesterol, LDL cholesterol, triglycerides) will only be done at weeks: 288, 336, 384, 432 and 480.
- Obtain blood sample for acute phase reactant: hs-CRP.
- Before dosing, obtain serum sample for PK (sarilumab) and for anti-sarilumab antibody.
- Obtain blood sample for ANA at week 288, 336, 384, 432 and 480, or sooner if clinically indicated.
- Obtain urine sample for urine pregnancy test for female of child bearing potential. The patients should be instructed to do the urine pregnancy test at home on a monthly basis during the intervals in between on-treatment clinic visits for the duration of the treatment period. In case of a positive pregnancy test, the patient should be advised to stop the IMP and to contact immediately her study doctor.
- Perform a complete joint examination to assess tender and swollen joints. Only the 28 joints required for DAS28 calculation need to be evaluated (see [Appendix B](#)).
- Ask the patient to complete patient's global assessment.
- Dispense Investigational Product (12-week supply) and remind instructions on self-injection and dosing; and provide self-injection diary.
- The study coordinator or designee will administer the subcutaneous injection (if 14±3 days from last administration) and will observe the patient for 30 minutes.

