- k Lipids (fasting): Total cholesterol (TC), High-Density Lipoprotein (HDL) cholesterol, Low-Density Lipoprotein (LDL) cholesterol, triglycerides, Apolipoprotein A, and Apolipoprotein B. After Week 264, lipids (excluding Apolipoprotein A, and Apolipoprotein B ) will only be assessed at Weeks 288, 336, 384, 432, 480 (including EOT if EOT is after Week 264)
- l Clinical chemistry (fasting): fasting glucose, total proteins, calcium, sodium, potassium, Lactate Dehydrogenase, (LDH), urea nitrogen and creatinine. Creatinine clearance will be calculated during the study if clinical indicated.
- m Deleted.
- n ANA titer will be done at V1/V2 ( ie the last treatment visit from the initial study), at Week 48, 96, 144, 192, 240, 264, 288, 336, 384, 432, 480 and EOT visit , or sooner if clinical indicated (Anti-ds-DNA only if ANA titer is  $>1:160$ )
- o Dipstick urinalysis for: specific gravity, pH, glucose, blood, ketones, proteins, bilirubin, urobilinogen, nitrite, leukocytes. If any parameter is abnormal, a urinalysis sample should be sent to central laboratory for testing. If positive for proteins, microscopic analysis will be performed by central laboratory.
- p After Visit 7 (Week 12) between study visits the patient will have a urine pregnancy test at home on a monthly basis. Patients will be given sufficient urine pregnancy kits to take home at each successive visit for monthly testing up until the final treatment visit. When the testing coincides with a clinical visit as indicated in the flow chart, the results should be reported in the e-CRF. No pregnancy test kits will be dispensed at EOT.
- q ECG to be done at Weeks 48, 96, 144, 192, 240, 264 or EOT; No ECG will be done after Week 264 including EOT if EOT is after Week 264
- r Rheumatoid factor only at Weeks 48, 96, 144, 192, 240, 264 or EOT; No Rheumatoid factor will be assessed after Week 264 including EOT if EOT is after Week 264
- s If throughout the study a serious adverse event (SAE) occurs in a patient, blood samples should be collected for sarilumab at or near the onset and completion of the occurrence of the event, if possible. The exact date of sample collection and last dose must be recorded on the eCRF.
- t Serum sample for biomarkers to be collected for all patients except EFC13752: at V1/V2 (ie, the last treatment visit from the initial study), as well as Week 2, Week 12, and Week 48.

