## 2.4.2 Prior or concomitant medications

Prior medications are those the patients used prior to first IMP intake in LTS11210. The data before enrollment were collected and reported in the previous studies. However the data from enrollment up to the time of first IMP intake will be reported in LTS11210 database.

Prior and concomitant medications in LTS11210 will be presented based on the enrolled population.

Medications will be summarized by treatment received according to the WHO-DD dictionary, considering the first digit of the ATC class (anatomic category) and the first three digits of the ATC class (therapeutic category). All ATC codes corresponding to a medication will be summarized. Patients will be counted once in each ATC categories (anatomic or therapeutic) linked to the medication, therefore, patients may be counted several times for the same medication. In addition, the summaries for concomitant DMARDs (MTX, non-MTX DMARDs), folic acid, NSAIDs, corticosteroids, and lipid modifying agents will also be provided.

The tables for concomitant medications will be sorted by decreasing frequency of anatomic category followed by all other therapeutic classes. In case of equal frequency regarding anatomic categories (respectively therapeutic categories), alphabetical order will be used.

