## **2.5.4 Windows for time points**

For efficacy parameters (except X-ray), a discontinuation visit (EOT, Visit 49) will be mapped to the scheduled visit for the analyses. If a discontinuation visit happens at a regular visit, then the visit number will be reassigned as the regular visit number where an assessment is planned. If a discontinuation visit happens between 2 regular visits, then the visit number will be reassigned to the next visit number where an assessment is planned. For example, if a discontinuation visit happens between Visits 9 and 10, then the visit number will be reassigned as 10. Similarly, the EOT visit (Visit 49) for patients who complete the study with 260-week treatment duration per Protocol Amendment 8, will be mapped to the Visit 28.

For X-ray data, the linear extrapolation method for the modified total Sharp score, the erosion score, and the joint space narrowing score will use true date to extrapolate missing values at Weeks 48, 96, 144, and 192 with no visit remapping.

All efficacy analyses will be performed by the nominal visit number and no visit window will be defined.

For safety assessments, the reference date for the derivation of relative days of events or findings will be the date of first drug intake as documented in the study drug administration page of the eCRF. Selected safety variables will be summarized using the visit window defined in [Table 6](#) for the by-visit descriptive analysis. Note that only the laboratory measurements performed at the central laboratory will be used for the by-visit descriptive analysis. All available values obtained between two visits including unscheduled measurements will be assigned to the appropriate visit window. The following rule will be applied when mapping the measurements to the visit:

1. When a patient has more than one measurement on the same laboratory parameter (or vital sign or ECG) on the same date, then the one with the later/largest sample ID will be used.
2. For the same laboratory parameter (vital sign or ECG), if a patient has more than one measurement at different dates within the same visit window, the scheduled measurement that is closest to the target date will be used. If there is no scheduled measurement within the visit window, the unscheduled measurement that is closest to the target date will be used.

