**Table 6 - Study window (in days) for safety variables in LTS11210**

Week (Visit)	Target day	Blood hematology Blood liver function	Blood chemistry a /Urinalysis	Vital signs	ECGs	PK/ADA/ Serum IL-6 b sample	ANA/Anti-ds-DNA/ Rheumatoid factor c
Baseline d (-1)							
0 e (1,2 or 1/2)	1						
2 (3)	15	2-21					
4 (4)	29	22-35		2-42		2-56	
6 (5)	43	36-49					
8 (6)	57	50-63	2-70	43-70			
10 (6.1)	71	64-77					
12 (7)	85	78-126	71-126	71-126		57-126	
24 (8)	169	127-210	127-210	127-210		127-210	
36 (9)	253	211-294	211-294	211-294		211-294	
48 (10)	337	295-378	295-378	295-378	2-504	295-378	2-504
60 (11)	421	379-462	379-462	379-462		379-462	
72 (12)	505	463-546	463-546	463-546		463-546	
84 (13)	589	547-630	547-630	547-630		547-630	
96 (14)	673	631-756	631-756	631-756	505-840	631-756	505-840
120 (16)	841	757-924	757-924	757-924		757-924	
144 (18)	1009	925-1092	925-1092	925-1092	841-1176	925-1092	841-1176
168 (20)	1177	1093-1260	1093-1260	1093-1260		1093-1260	
192 (22)	1345	1261-1428	1261-1428	1261-1428	1177-1512	1261-1428	1177-1512
216 (24)	1513	1429-1596	1429-1596	1429-1596		1429-1596	
240 (26)	1681	1597-1764	1597-1764	1597-1764	1513-1764	1597-1764	1513-1764
264 (28)	1849	1765-1932	1765-1932	1765-1932	≥1765	1765-1932	1765-1932
288 (30)	2017	1933-2100	1933-2100	1933-2100		1933-2100	1933-2184
312 (32)	2185	2101-2268	2101-2268	2101-2268		2101-2268	
336 (34)	2353	2269-2436	2269-2436	2269-2436		2269-2436	2185-2520
360 (36)	2521	2437-2604	2437-2604	2437-2604		2437-2604	
384 (38)	2689	2605-2772	2605-2772	2605-2772		2605-2772	2521-2856
408 (40)	2857	2773-2940	2773-2940	2773-2940		2773-2940	
432 (42)	3025	2941-3108	2941-3108	2941-3108		2941-3108	2857-3192
456 (44)	3193	3109-3276	3109-3276	3109-3276		3109-3276	
480 (46)	3361	3277-3444	3277-3444	3277-3444		3277-3444	3193-3486
504 (48)	3529	3445-3570	3445-3570	3445-3570		3445-3570	
516 (49)	3613	≥3571	≥3571	≥3571		≥3571	≥3487

a Lipids profile (metabolism) was also performed at Weeks 4 and 8 (Week 4: 2-42 days, Week 8: 43-70 days)

b Serum IL-6 sample is collected at Weeks 0, 4, 12, 24, 36, and 48 only; ADA at Week 12 (2-126 days) due to no ADA at Week 4.

c Anti-ds-DNA only if ANA titer is >1:160; Rheumatoid factor only at Week 0, 48, 96, 144, 192, 240, and 264 (or EOT).

d Baseline from previous studies

e The value at Week 0 is defined as the last non-missing value in the measurements collected at Visits 1, 2 and/or 1/2, and/or EOT visit in previous studies.

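### After Week 264, 5 of the 10 by-visit lipid windows to Week 504 hold no scheduled on-treatment draw, so their means would come only from end-of-treatment and unscheduled values

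*SAP*

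**What the plan says.** SAP 2.4.4.3 asks for "The summary statistics (including number, mean, median, standard deviation, minimum and maximum) of all laboratory variables (central laboratory values and changes from baseline" at baseline, each post-baseline time point and endpoint. SAP 2.5.4 places central-laboratory values for the by-visit tables using Table 6: "All available values obtained between two visits including unscheduled measurements will be assigned to the appropriate visit window".

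Table 6 has no lipid column. Lipids appear only in note a: "Lipids profile (metabolism) was also performed at Weeks 4 and 8 (Week 4: 2-42 days, Week 8: 43-70 days". Apart from those two weeks they follow the blood chemistry column, which has a separate window for each 24-week visit through Week 504 and an open-ended Week 516 row.

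The draw schedule after Week 264 is sparser. Note k of the SAP flow chart (1.4.3.2) says that lipids "will only be assessed at Weeks 288, 336, 384, 432, 480 (including EOT if EOT is after Week 264". Protocol 12.1.11 agrees: "lipids (only TC, HDL cholesterol, LDL cholesterol, triglycerides) will only be done at weeks: 288, 336, 384, 432 and 480". Protocol 12.1.12 adds a lipid profile at an EOT visit after Week 264. Under Protocol 12.1, EOT can fall "At any visit after Week 264 once sarilumab is commercialized in their country", at study closure in 2020, or at premature discontinuation.

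ANA has the same late schedule. Note n lists it "at Week 48, 96, 144, 192, 240, 264, 288, 336, 384, 432, 480 and EOT visit". For ANA, Table 6 uses wider windows after Week 264, one for each of the five scheduled weeks.

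**The concern.** From Week 288 lipids are drawn every 48 weeks, but the rows that report them stay 24 weeks apart. Every second row then has no on-treatment visit to feed it. Because SAP 2.5.4 sends every available value to a window, those rows are filled by whatever else exists: EOT draws and unscheduled central samples. Reading down the table, the population would switch at each row between everyone still on treatment and patients at their last treatment visit or being re-tested. The table gives the number of values, so a drop would be visible, but nothing tells the reader who those patients are.

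These rows are likely to be read. Protocol 4.1.2 lists elevated LDL cholesterol among the expected laboratory findings, Protocol 10.2.10 says that the cardiovascular effect of the lipid rise is unknown, and the primary objective is long-term safety.

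**Working it through.** **Inputs.** Windows and target days are from SAP Table 6 (blood chemistry column, with note a for Weeks 4 and 8). Lipid draw weeks are from Protocol 12.1.4 to 12.1.12 and flow-chart note k.

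**Reproducing the plan's target days.** Target day = 7 × week + 1. Week 288 gives 7 × 288 + 1 = 2017 and Week 504 gives 7 × 504 + 1 = 3529. All ten stated target days from Week 288 to Week 504 are reproduced exactly.

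**Placing the draws.** Each scheduled lipid day (±3 days) was placed in its window. EOT is shown at nominal 12-weekly visits, because Protocol 12.1 sets EOT 12 weeks after the visit at which the patient is told.

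| Window (week) | Days | Scheduled on-treatment lipid draw | EOT weeks that fall in it |
|---|---|---|---|
| 288 | 1933–2100 | Yes | 276, 288 |
| 312 | 2101–2268 | None | 300, 312 |
| 336 | 2269–2436 | Yes | 324, 336 |
| 360 | 2437–2604 | None | 348, 360 |
| 384 | 2605–2772 | Yes | 372, 384 |
| 408 | 2773–2940 | None | 396, 408 |
| 432 | 2941–3108 | Yes | 420, 432 |
| 456 | 3109–3276 | None | 444, 456 |
| 480 | 3277–3444 | Yes | 468, 480 |
| 504 | 3445–3570 | None | 492, 504 |

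Five of the ten windows have no scheduled on-treatment draw. An EOT value can fall in any of the ten. Even the Week 336 row can take one from 12 weeks earlier: an EOT at Week 324 is day 7 × 324 + 1 = 2269, the first day of that window.

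**Whole-table count.** Lipid windows: 2 (Weeks 4, 8) + 8 (Weeks 12 to 96) + 7 (Weeks 120 to 264) + 10 (Weeks 288 to 504) + 1 (Week 516) = 28. Scheduled post-baseline on-treatment draws: 3 (Weeks 4, 8, 12) + 7 (Weeks 24 to 96) + 7 (Weeks 120 to 264) + 5 = 22. The difference of 6 is the five windows above plus the Week 516 row, which is the EOT visit by design.

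**Up to Week 264.** 2 + 8 + 7 = 17 windows, and all 17 hold a scheduled draw.

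**Comparison with ANA.** The ANA windows after Week 264 are 1933–2184, 2185–2520, 2521–2856, 2857–3192 and 3193–3486. Each contains exactly one of the five scheduled days (2017, 2353, 2689, 3025, 3361). The late schedule was carried into Table 6 for ANA but not for lipids.

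**The case against.** The strongest reply is that Table 6 is only a grid for assigning values, not a list of rows to print. SAP 2.5.4 applies it to selected safety variables. Urinalysis shares the chemistry column through Week 516 although Protocol 10.1 stops it after Week 264, so a window need not imply a row. The lipid schedule is in the SAP's own flow chart, and n is always shown. This does not remove the problem. SAP 2.4.4.3 asks for statistics at each post-baseline time point and SAP 2.5.4 sends all available values to a window. Urinalysis has no planned draw after Week 264, whereas lipids have a planned EOT draw that will populate the unsupported windows.

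Three parts of the reply do stand. The windows are not empty by plan, because EOT draws are scheduled. The EOT group in a window need not be small: exits follow commercial launch country by country, and at closure all remaining patients have EOT within three months. Many of these exits are administrative, with no stated link to lipids, so no bias of known direction is shown.

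A reader might infer two stronger points. One is that the by-visit means fail to show the long-term lipid course. The documents do not support that: all 17 windows to Week 264 are sound and five scheduled points follow. The other is that the means are wrong because they include patients on lipid-lowering therapy. Protocol 8.8.2 and 10.2.10 direct such therapy, so observed means validly describe lipids under the study's own management. SAP 2.4.2 already plans a summary of lipid-modifying agents, and the documents give no figure from which to size any masking.

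**Conclusion.** The concern holds as a mismatch within the SAP, limited to by-visit lipid summaries after Week 264. Five of the ten windows from Week 288 to Week 504 would give means based only on EOT and unscheduled central values, set between means for all patients still treated. This rests on reading note a of Table 6 as placing lipids in the chemistry column, which is the only column that fits.

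The consequence is misleading rows in a descriptive table. How many patients it touches cannot be stated, because the number treated beyond Week 264 is not given. The PCSA incidence, shift tables, lipid-elevation AESI and adjudicated MACE summaries do not use these windows. No test, primary endpoint or decision rule depends on them.

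**What to change.** In SAP 2.5.4 and Table 6, state that by-visit lipid summaries after Week 264 are reported only at Weeks 288, 336, 384, 432 and 480, from on-treatment values in their existing windows. Show EOT lipid values as a separate row, not mapped to any visit window. The planned endpoint row is not a substitute: SAP 2.4.4 defines it as the value on the day of the last dose or the closest one before it, which need not be the EOT draw.

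Copying the ANA windows is not recommended. An EOT at Week 312 is day 2185, the first day of the ANA-type Week 336 window, so that value would enter the Week 336 mean from 2353 − 2185 = 168 days away. That would blend leavers into otherwise clean rows.

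The cost is a table note and one extra row per lipid table, from data already collected. Unscheduled central draws in the dropped windows would leave the by-visit tables but remain in the PCSA analysis. Showing n (%) on lipid-modifying agents beside the means would help a reader, but it is optional and not part of this error.
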